#### 9.2.2. Relative error and trend accuracy calculations

In order to compute error, discrete time points along the continuous trances will be selected in a consistent fashion. The data points will be selected with a minimum of 5 min interval.

Relative error in rSO2 is computed on a sensor by sensor (i.e. subject by subject) basis.

Relative error is defined to be the relative difference of the test sensor and reference sensor rSO2.

Trending Accuracy is defined as root-mean-squared relative error of discrete data points across subjects.

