**1. PURPOSE**

This study is designed to evaluate the trending accuracy of O3 system's measurement of oxygen saturation in somatic sites.

The INVSENSOR00038 is Masimo's O3 system, which has been cleared by the FDA for rSO2 measurements in the cerebral tissue. The INVSENSOR00038

and is considered an investigational device when placed over skeletal muscle. The values obtained by the INVSENSOR00038 will be compared to reference values.

This is a nonrandomized study wherein all subjects receive both the somatic sensor (INVSENSOR00038) and one FDA-cleared device sensor. Data using the sensors will be collected from healthy volunteers undergoing a desaturation procedure. Desaturation will be conducted by reducing the concentration of oxygen the study subject breathes in a controlled manner to obtain noninvasive regional oxygen saturation readings, rSO2, at various levels.

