**Outcome Measure:**

This study will evaluate the trending accuracy of the INVSENSOR00038 relative to the reference value obtained from the comparative FDA-cleared device.

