## Desaturation Validation of INVSENSOR00038

7.4.4 Local anesthetics such as lidocaine, ethyl chloride spray, or Pain Ease skin refrigerant spray may be used in the event that an IV is placed to numb the site. Subjects will be given the option to have lidocaine or numbing spray be used during IV placement for the purpose of making catheter placement more comfortable for the subjects.

7.4.5 Sensor of the control device will be placed on one side of the somatic site and INVSENSOR00038 will be placed on the other side of the somatic site. Subjects may be asked to shave the area prior to sensor placement. If the subject declines to shave they may be kept from participating in the study.

Upon indication the subject is comfortable, a gas mixture will be administered. The proportion of oxygen in this mixture will be decreased in a controlled manner to lower the subject's blood oxygen saturation. The lowest targeted value will be [REDACTED] oxygen saturation as measured by [REDACTED]. Note: At any point in the study, if the subject feels uncomfortable, the subject will be given 100% oxygen [REDACTED]

7.4.14 The study will end with several minutes at a FiO2 greater than room air (>21%) to help the subject re-saturate after the procedures.

7.4.16 At the conclusion of the procedure, the sensors/devices, and IV(s) will be removed and the subject will be allowed to leave after medical personnel determine it is safe to do so.

7.4.17 Study staff may take one final blood draw 1-4cc to verify the subjects blood values are within normal range (eg. pH, Glucose, etc.). These values will be assessed by a physician and the subject will then be cleared to leave the study space.

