## 9.2. Statistical Analysis

INVSENSOR00038 is placed on the somatic site. Reference sensor from the control device is placed on the somatic site on the contralateral side.

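### As Section 9.2.2 reads, Trending Accuracy counts a constant test-reference offset as trend error, and its single figure cannot separate that offset from failure to follow the desaturation

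*Combined protocol and SAP*

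**What the plan says.** Section 1 gives one aim: "This study is designed to evaluate the trending accuracy of O3 system's measurement of oxygen saturation in somatic sites". The Outcome Measure paragraph repeats it: "This study will evaluate the trending accuracy of the INVSENSOR00038 relative to the reference value obtained from the comparative FDA-cleared device". No readable section names agreement in level as an outcome, and Section 13.1 frames the expected benefit in terms of trend accuracy.

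Section 9.2.2 defines the statistic in three steps:

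- Points: "The data points will be selected with a minimum of 5 min interval".
- Error: "Relative error is defined to be the relative difference of the test sensor and reference sensor rSO2", with the added statement "Relative error in rSO2 is computed on a sensor by sensor (i.e. subject by subject) basis".
- Summary: "Trending Accuracy is defined as root-mean-squared relative error of discrete data points across subjects".

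It gives no equation. The denominator is not stated, and no baseline value, change score or subject mean is mentioned.

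On placement, Section 7.4.5 says "Sensor of the control device will be placed on one side of the somatic site and INVSENSOR00038 will be placed on the other side", and Section 9.2 confirms it: "Reference sensor from the control device is placed on the somatic site on the contralateral side". Section 6 lists the reference as a tissue oximetry system cleared for somatic use, so the comparison is between two oximeters.

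**The concern.** Trending asks whether the test sensor rises and falls with the reference. A relative difference taken at each time point also asks whether the two sensors read the same level. Two devices of different make, on opposite sides of the body, may differ by a roughly constant amount for reasons unrelated to tracking. On the plain reading that amount enters the statistic in full.

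A poor score could then come from a sensor that follows every change but reads a few points high or low, or from one that responds sluggishly. These lead to different conclusions about the only question the trial asks, and the one pooled figure cannot tell them apart.

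**Working it through.** **The plan's own figure.** There is none to reproduce: the acceptance criteria (Section 8) and sample size (Section 9.1) are redacted. The check applies the readable definition to assumed traces.

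**Formula, plain reading, with the reference as assumed denominator.** e = 100 × (test − ref)/ref, and Trending Accuracy = √mean(e²). Since mean(e²) = (mean e)² + var(e), any average offset enters the score.

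**Assumed inputs (none is in the documents).**

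- Reference A: 70, 70, 68, 66, 63, 60, 70, 70.
- Reference B: 70, 70, 65, 60, 55, 50, 70, 70.
- Test = 70 + s × (ref − 70) + offset, where s = 1 is a perfect tracker, s = 0.5 shows half of every change, and s = 0 is frozen at baseline.

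**Step 1: one score, two explanations.**

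- In A, the frozen sensor with no offset has errors of 2.94, 6.06, 11.11 and 16.67% at the four desaturated points and 0 at the other four. The squares sum to 446.6; √(446.6/8) = 7.5%.
- A perfect tracker with a constant offset scores |offset| × RMS(100/ref). RMS(100/ref) is 1.497 in A and 1.605 in B. In A, an offset of 5.0 points gives 5.0 × 1.497 = 7.5%, the same score.
- The other equal-score pairs, perfect tracker with offset against under-responder without, are: in A, 3.7% (2.5 points, or half-response); in B, 9.2% (5.7 points, or half-response) and 18.3% (11.4 points, or frozen).

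**Step 2: sensors sharing the same offset (perfect / half / frozen).**

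| Offset | A, % | B, % |
|---|---|---|
| 0 | 0.0 / 3.7 / 7.5 | 0.0 / 9.2 / 18.3 |
| +7 | 10.5 / 13.2 / 16.4 | 11.2 / 18.9 / 27.5 |
| −7 | 10.5 / 8.5 / 7.9 | 11.2 / 7.9 / 12.9 |
| half of subjects +7, half −7 | 10.5 / 11.1 / 12.9 | 11.2 / 14.5 / 21.5 |

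The order is right at 0, at +7 and in the mixture. It can reverse only when the test reads below the reference: by more than about 1.9 points (half-response) or 3.8 (frozen) in A, and 4.0 or 7.9 in B.

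**Step 3: the same sensors with the offset removed.**

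- Change score: (test − its baseline) − (ref − its baseline), with baseline the mean of points 1 and 2 and the RMS taken over points 3 to 8. Results are 0.0 / 2.7 / 5.3 points in A and 0.0 / 5.6 / 11.2 in B, identical at offsets of −7, 0 and +7.
- Subtracting each subject's mean test-minus-reference difference instead, over all eight points: 0.0 / 1.8 / 3.6 points in A and 0.0 / 3.7 / 7.4 in B.

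**Step 4: where to measure the offset.** With a true offset of +7 in A, the mean difference over all eight points is 7.0 / 8.4 / 9.9. It absorbs failure to track, so the offset is better taken from a pre-desaturation period.

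**The case against.** **The wording may already remove the offset.** Relative could mean relative to the subject's own baseline, and the subject-by-subject sentence does more work on that reading. If that is what is meant, the offset objection largely falls and only the formula is missing. This stands as a real possibility. The plain wording, however, compares two sensors, and computing by subject need not mean centring by subject.

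**Text is missing.** Sections 8 and 9.1 are redacted, Section 9.3 on bias has no readable body, and the steps between 7.4.5 and 7.4.14 are not visible. A baseline period or offset handling may sit there. This also stands: a reader might infer that the plan overlooks baseline altogether, but the documents show only that 9.2.2 as readable does not use one.

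**The metric is not blind to tracking.** A reader might infer that it ignores tracking or generally favours unresponsive sensors. It does not. Under-response raises the score at a shared zero or positive offset, reversal needs a sufficiently negative offset, and a very low score requires both a small offset and good tracking.

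**The illustration is assumed.** In the mixed-offset case, perfect and half-response differ by only 0.6 percentage points in A but by 3.3 in B (14.5 − 11.2), so the smallness of the gap comes mainly from the shallow trace. Half the points sit at 70, and a recovery period of several minutes may not yield two points at least 5 minutes apart. Dropping the two recovery points widens the gap in A only to 0.9 and leaves the break-even offsets unchanged.

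**Conclusion.** The concern holds for the definition as readable. A constant between-device or left-right difference is counted as trend error, and the single score does not separate it from failure to follow the desaturation. That follows from the algebra of a pointwise relative difference, not from the chosen traces.

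The size in this trial is unknown. The 7.5% equivalence, and the 1.5 (A) or 1.6 (B) percentage points that each point of constant offset adds to a perfect tracker's score, rest on assumed traces, constant offsets and the reference as denominator.

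A reader might go on to infer that the device would be wrongly passed or failed. The documents do not support that, because the limit, the depth of desaturation and the actual offset are not visible. Nor do they show whether the redacted limit concerns level agreement or trending. The point is worth fixing before analysis, with medium confidence given the ambiguous wording and the unreadable sections.

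**What to change.** In Section 9.2.2, write the formula with its denominator and say whether each subject's baseline or mean difference is removed. If it is, no further change is needed.

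If it is not, keep the existing RMS and pre-specify alongside it, from the same recordings:

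- (a) An offset-removed RMS: change from each sensor's own averaged pre-desaturation value or, if no baseline period is recorded, the RMS after subtracting each subject's mean difference. Fix absolute or percent change in advance.
- (b) The mean and between-subject SD of the pre-desaturation test-minus-reference offset. If only an all-point mean difference is available, label it as such, since it absorbs some tracking failure.

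Read the tracking conclusion with (a) in view. A pooled within-subject slope of test change on reference change is an optional supplement; noise in the reference pulls it below 1. Before the data are analysed, the sponsor should confirm which quantity the acceptance limit applies to.

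The cost is SAP wording and a little extra analysis, with no new subjects or measurements. Baseline noise enters (a); averaging the baseline reduces it. The choice of scale has a price either way. Absolute change penalises a purely proportional sensor (1.15 × reference scores 0.8 points in A and 1.7 in B), while percent change does not. Percent change, in turn, gives a perfect tracker at +7 a score of 0.7 (A) or 1.5 (B) percentage points instead of 0.

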#### 7.4. PROCEDURES

- 7.4.1. Standard hospital-type monitors will be placed on the subject, including ECG, blood pressure, and a reference pulse oximeter for safety monitoring by medical staff.
- 7.4.2. Proprietary Masimo data collection software will be used to verify all oximeters are reading. If not, proper sensor positioning will be checked and sensors may be repositioned, as needed.
  - 7.4.2.1 Pulse oximeter output values (e.g., SpO2, Pulse rate) will be recorded using the proprietary Masimo data collection software. These values match the values calculated by the instrument at runtime.
  - 7.4.2.2 Raw absorbance data from the noninvasive device(s) will also be recorded using the data collection software.
- 7.4.3. A peripheral venous line(s) will be placed in the subject's arm. One or more venous sampling catheters may be placed and used for the qualifying venous blood draw and/or for safety or clinical intervention required during the study.

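### Does the single pooled RMS in section 9.2.2, with no subject-level interval and no breakdown by phase, need to be changed?

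*Combined protocol and SAP*

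**What the plan says.** Section 9.2.2 takes discrete points from each continuous trace. On spacing it says "The data points will be selected with a minimum of 5 min interval", and on choice it says "discrete time points along the continuous trances will be selected in a consistent fashion". The error at a point is defined thus: "Relative error is defined to be the relative difference of the test sensor and reference sensor rSO2". The level of calculation is given as "Relative error in rSO2 is computed on a sensor by sensor (i.e. subject by subject) basis". The summary is then "Trending Accuracy is defined as root-mean-squared relative error of discrete data points across subjects". The Outcome Measure paragraph under section 1 names trending accuracy as what the study evaluates, so this number carries the result.

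Three other places bear on the point. Section 1 says that oxygen is lowered "to obtain noninvasive regional oxygen saturation readings, rSO 2 , at various levels". Step 7.4.14 closes the session with a period at an inspired oxygen fraction "greater than room air (>21%) to help the subject re-saturate after the procedures". Step 7.4.2.1 adds: "Pulse oximeter output values (e.g., SpO 2 , Pulse rate) will be recorded".

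Sections 8 (acceptance criteria) and 9.1 (sample size) are redacted. Section 9.3 shows a heading only, the schedule under 7.1 is blank, and steps 7.4.6 to 7.4.13 and 7.4.15 are not in the public text.

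**The concern.** The phrase about working subject by subject governs how each error is computed. The summary still pools all points, and three worries follow.

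- **Precision.** The two sensors sit on opposite sides of the same person, so a subject may carry a lasting offset between them. Points within a subject would then be correlated, and the RMS would be less precise than the number of points suggests.
- **Interpretation.** If error grows as saturation falls, points near baseline or during recovery pull the single figure down, and a reader cannot see this.
- **Definition.** A relative difference needs a denominator, and the visible text does not name one.

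At stake would be whether a favourable RMS can be taken at face value, and whether it speaks for the low levels that the procedure sets out to reach.

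**Working it through.** **Inputs.** The documents give the definition of the summary, the minimum spacing, and the fact that points come from continuous traces. They show no sample size, number of points, acceptance limit, standard deviation or session length. There is therefore no figure of the plan's own to reproduce, and every magnitude below rests on assumed inputs.

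**Step 1: is the pooled figure biased?** Let q_i be the sum of squared relative errors and m_i the number of points in subject i. The plan's figure is the square root of M = sum(q_i)/sum(m_i). With equal m_i, the expectation of M is the true mean square whatever the within-subject correlation. Taking the root adds a small downward bias of about SD²/(2 × RMS). In the worst case of the table below, SD = 2.29 × 0.25 = 0.57, and the bias is 0.57²/10 = 0.03 percentage points. With unequal m_i, subjects with more points weigh more. That is a choice of weighting, and it misleads only if error is related to the point count.

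**Step 2: precision.** With normal errors and a shared subject effect, squared errors within a subject have correlation r², so

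SD(RMS) ≈ RMS/√(2nm) × √(1 + (m − 1)r²).

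For n = 20, m = 10 and RMS = 5%, the first factor is 5/√400 = 0.25. The table sets the second factor beside 20,000 simulated studies per row.

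| r | √(1 + 9r²) | simulated SD ratio | 95% range of RMS | coverage if points are taken as independent |
|---|---|---|---|---|
| 0.1 | 1.04 | 1.05 | 4.5-5.5% | 94.0% |
| 0.3 | 1.35 | 1.33 | 4.4-5.7% | 86.1% |
| 0.5 | 1.80 | 1.78 | 4.2-5.9% | 72.6% |
| 0.7 | 2.33 | 2.29 | 3.9-6.2% | 60.3% |

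The last column would be a serious fault in an interval built that way, but the visible plan contains no such interval. An analyst who wants one can form it from the q_i and m_i. A t interval on the log of M, with the subject as unit, covers 89.6-94.7% with 10 subjects, 91.3-94.7% with 20 and 92.2-94.8% with 30. With 10 subjects and unequal counts it covers 88.7-94.6%.

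**Step 3: mixing phases.** Suppose a sensor registers only half of each fall from a baseline of 70%. At reference values of 68, 66, 63 and 60% the differences are 1, 2, 3.5 and 5 points. Divided by the current reference, the errors are 1.47, 3.03, 5.56 and 8.33%, with a sum of squares of 111.65.

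- Four falling points: √(111.65/4) = 5.28%.
- One zero-error point added: √(111.65/5) = 4.73%, a fall of 1 − √(4/5) = 11%.
- Two added: √(111.65/6) = 4.31%, a fall of 1 − √(4/6) = 18%.

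Now add an independent subject offset with RMS 6%. The three figures become √(27.91 + 36) = 7.99%, √(22.33 + 36) = 7.64% and √(18.61 + 36) = 7.39%, which are falls of about 4% and 8%. If error is the same at every level, the fall is zero. Nothing visible says that error differs by level.

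The closing recovery period lasts some minutes, and points are at least 5 minutes apart. It may supply few points or none, and the text does not show whether it belongs to the analysed trace.

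**Step 4: the denominator.** With the baseline of 70% as divisor, the errors in Step 3 are 1.43, 2.86, 5.00 and 7.14%, and the RMS of the four falling points is 4.64% against 5.28%. The choice moves this example by 5.28 − 4.64 = 0.64 percentage points. Because the definition compares test with reference, dividing by the concurrent reference value is the ordinary reading.

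**The case for a change.** The best case for a change is this. The RMS is the sole outcome, nothing visible says how uncertain it is, and the desaturation is done to reach a range of levels. Two or three sentences and some code on data already recorded would let a reader judge both. SpO2 is recorded apart from the two rSO2 values under comparison, so it could define the levels without circularity. A cross-reference in 9.2.2 would help even if hidden text covers the matter.

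Part of this stands. The description of the visible text is accurate, and a subject-level interval with a descriptive table is good practice. The unstated denominator is the firmest of the three points, since it affects the figure itself.

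The rest does not carry. Acceptance criteria and a sample size justification are where an interval, an allowance for repeated points or a level-specific limit would normally appear, and both are blacked out. The missing steps of 7.4 are where levels and sampling would be described. What is redacted cannot be counted as absent. Section 1 gives trending accuracy as the purpose, and the phrase about levels describes what the procedure does. No visible text makes accuracy at the lowest level an objective. The phase example was also built to show dilution, by pairing a half-response sensor with points of exactly zero error.

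**Conclusion.** No change to the plan follows. An analyst who follows 9.2.2 as written obtains a valid pooled RMS. The additions would leave that figure and any pass rule as they are, so they are optional reporting. The gap is one that analysts can fill sensibly: divide by the reference value, give an interval with the subject as unit, and tabulate by recorded SpO2 or phase, with counts, if the data allow.

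The size is uncertain and may be small. With 20 subjects and 10 points each, repeated points widen the spread of the RMS by a factor of 1.05 at r = 0.1 and 2.29 at r = 0.7. Phase mixing lowers the figure by 18% at most in the constructed example and by nothing under equal error. These values rest on an assumed sample size, point count, correlation, true RMS and error pattern, none of which the public documents give. The conclusion would be different if the unredacted text proposed an interval or pass rule that counted points as independent; nothing visible suggests that it does.

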#### 9.3. Measures taken to minimize/avoid bias:

#### 9.4. Expected drop out rates

Subjects may not complete the study for various reasons, such as a clinical screening test failure, unable to complete desaturation

### 10. ADVERSE EVENTS

Definitions:

Adverse event: Any untoward medical occurrence in a subjects, users or other persons, whether or not related to the medical device under study.

Device-related adverse event: Adverse event related to, associated with, or caused by, the use of a medical device under study, including but not limited to events that may have been attributed to the device because of device failure or malfunction, improper or inadequate design, manufacture or user error.

Device deficiency: Inadequacy of a medical device with respect to its identity, quality, durability, reliability, safety or performance. Device deficiencies include malfunctions, use errors and inadequate labeling.

Device deficiencies will be reported according to department procedures.

Serious adverse event: Adverse event that: a) led to death, b) led to serious deterioration in the health of the subject, that resulted in: (i) a life-threatening illness or injury, (ii) a persistent or significant impairment of a body structure or a body function, (iii) in-patient or prolonged hospitalization, or (iv) medical or surgical intervention to prevent life-threatening illness or injury or permanent impairment to a body structure or a body function, or c) led to fetal distress, fetal death or a congenital abnormality or birth defect. NOTE: Planned hospitalization for a pre-existing condition, or a procedure required by the clinical investigational plan, without serious deterioration in health, is not considered a serious adverse event.

All adverse events, including inter-current illnesses will be reported and documented as described below.

#### 10.1. Adverse Events

**Desaturation Validation of INVSENSOR00038**

All adverse events that occur during the study shall be recorded on the Case Report Form even if the investigator/study staff assess the adverse event as unlikely to be causally related to the test device or study procedures.

